infection. They will be assigned to receive COVID-19 vaccine under EUA dosing (as programmatically outlined in Table 9. Additional pools of subjects can be included if needed as additional COVID-19 vaccines are awarded EUA. These pools of participants were to be assigned a novel homologous or heterologous variant boost or heterologous platform boost at a minimum of 12 weeks following receipt of EUA dosing and followed through 12 months after the last vaccination. As booster vaccines have been approved for individuals at an interval of 6 months from the primary series, under EUA, all Cohort 2 volunteers will be offered a booster of mRNA-1273 at the approved 50 mcg dose at Day 181 (+/- 30 days following dose 2 of their primary series. A telephone visit will occur one week after each primary EUA vaccination and one week after the booster dose. In person follow-up visits will occur on 14 days following completion of EUA vaccinations and on days 14, and 28 days after the booster dose, as well as 3, 6, and 12 months post the booster vaccination. A fourth dose of COVID-19 vaccine will be administered to participants using the Moderna mRNA-1273.222 bivalent vaccine at an interval of 4 to 12 months after the third dose (1st booster). In addition to the other immunologic assays planned for earlier parts of the study (including innate, cellular and humoral responses), samples also will be collected to measure mucosal immune responses before the booster dose and on days 14 and 28, and at 3 months and 6 months after the fourth dose (2nd booster). Due to the surge of the Omicron variant and breakthrough infections, volunteers who contract symptomatic or asymptomatic COVID-19 between completion of their EUA primary series and the scheduled booster dose will be allowed to continue in the study. The interval between the COVID-19 infection and booster dosing should be a minimum of 28 days.

Table 9: Cohort 2 Treatment Arms

Group	Sample Size	First Vaccination	Second Vaccination		Booster Vaccination 1		Booster Vaccination 2	
		Product and Dose	Interval	Product and Dose	Interval	Product and Dose	Interval	Product and Dose
1	250	100 mcg mRNA-1273	28 days	100 mcg mRNA-1273	~6 months	50 mcg mRNA-1273	4-12 months	50 mcg mRNA-1273.222

For both Cohorts 1 and 2, reactogenicity will be assessed at the above-mentioned visits and blood will be drawn for immunogenicity assays at the in-person follow-up visits.

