9.4.9 Exploratory Analyses

Summaries and analysis of cellular assay data will be presented for the mITT population. If there are protocol deviations which may affect the analysis, a PP analysis may also be performed.

The magnitude, phenotype and percentage of innate immune cells and SARS-CoV-2 specific B cells will be summarized at each timepoint by arm.

The magnitude, phenotype and percentage of cytokine producing S protein-specific T cells will be summarized at each timepoint by arm.

Breakthrough NAAT-confirmed, SARS-CoV-2 infections will be sequenced to assess for the presence of variant spike lineage proteins.

Summaries of mucosal immune responses, from nasal and salivary samples of participants in Cohort 2 who receive a second boost, will be summarized at each timepoint post-boost. Also, the correlation between the mucosal and the serological immune responses will be evaluated at each timepoint post-boost. The possibility of conducting these analysis by status of prior infection (as given by N-protein ELISA assay) will be assessed.

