2.1. Purpose of the Analyses

The analyses described in the SAPs for DMID 21-0012 will assess the immunogenicity and safety of delayed heterologous or homologous vaccine doses after EUA dosed vaccines and will be included in the clinical study report. Results from the DMID 21-0012 study will be reported in five complementary CSRs with each CSR having a corresponding SAP as described below:

- DMID 21-0012 CSR for Janssen Ad26.COV2.S: will focus on Cohort 1 study groups 4E, 5E, 6E (Janssen Ad26.COV2.S boost).
- DMID 21-0012 CSR for Moderna mRNA-1273: will focus on Cohort 1 study groups 1E, 2E, 3E (Moderna- mRNA-1273 100 mcg boost), 10E, 11E (Moderna- mRNA-1273.211), 12E, 13E, 14E (Moderna- mRNA-1273 50 mcg boost)
- DMID 21-0012 CSR for Pfizer BNT162b2: will focus on Cohort 1 study groups 7E, 8E, 9E (Pfizer/BioNTech –BNT162b2 boost)
- DMID 21-0012 CSR for Novavax NVX-CoV2373: will focus on Cohort 1 study groups 15E, 16E, 17E (Novavax NVX-CoV2373 boost)

 DMID 21-0012 CSR for Moderna – mRNA-1273, Cohort 2: will focus on Cohort 2 participants (Moderna- mRNA-1273 100 mcg prime, Moderna – 50 mcg mRNA-1273 first boost and Moderna – 50 mcg mRNA-1273.222 second boost

This SAP describes the statistical analysis that will be included in the DMID 21-0012 CSR for Janssen – Ad26.COV2.S. Specifically, the analyses will assess the co-primary objectives of DMID 21-0012, related to the safety and immunogenicity of Janssen Ad26.COV2.S vaccine administered as a booster after receipt of Moderna (Group 4E), Janssen (Group 5E) or Pfizer (Group 6E) EUA vaccinations.

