6.3. Analysis Populations

Analyses in the plan will only include participants who received the delayed Janssen-Ad26.COV2.S booster vaccine, study groups 4E, 5E and 6E. Participants will be grouped based on their initial EUA vaccination received for all analyses.

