6.3.4. Per Protocol Population

In the final analysis, protocol deviations will be reviewed to determine which protocol deviations may affect the analysis. The per protocol (PP) population will then be defined – and this includes all participants in the mITT subset with the following exclusions:

- Data from all available visits for participants found to be ineligible at enrollment.
- Data from all visits subsequent for the protocol deviations that are considered to affect the science.
- Data from any visit that occurs substantially out of window (i.e., 2x window):
 - Before Day 6 or after Day 10 for Day 8 Visit (Study Visit 2)
 - Before Day 11 or after Day 19 for Day 15 Visit (Study Visit 3)
 - Before Day 25 or after Day 33 for Day 29 Visit (Study Visit 4)
 - Before Day 77 or after Day 105 for Day 91 Visit (Study Visit 5)
 - o Before Day 153 or after Day 209 for Day 181 Visit (Study Visit 6)
 - Before Day 217 or after Day 329 for Day 273 Visit (Study Visit 7)
 - Before Day 310 or after Day 422 for Day 366 Visit (Study Visit 8)

Additional criteria, which do not strictly constitute protocol deviations, will also be applied for exclusion of participants or observations in the PP analysis of immunogenicity endpoints, as follows:

- Receipt of non-study COVID-19 vaccine any time after study vaccination.
- Receipt of seasonal influenza vaccine within 14 days after study vaccination.
- Breakthrough COVID-19 infection either self-reported or Positive N-antibody test.

The live-virus neutralization PP analyses will be based on a subset of 20 participants per study group that were randomly selected, stratified by age for this assay and who meet all criteria of the PP population.

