	BA.1	x (xx.x%)	x (xx.x%)	x (xx.x%)	x (xx.x%)
	BA.4/5	x (xx.x%)	x (xx.x%)	x (xx.x%)	x (xx.x%)
	XBB.1	x (xx.x%)	x (xx.x%)	x (xx.x%)	x (xx.x%)

Interval	PANGO Call	Group 4E [Dosed Janssen, Boost Janssen] (N=X)	Group 5E [Dosed Moderna, Boost Janssen] (N=X)	Group 6E [Dosed Pfizer, Boost Janssen] (N=X)	All Participants (N=X)
Day 182 to Day 273	D614G	x (xx.x%)	x (xx.x%)	x (xx.x%)	x (xx.x%)
(n=x)	Beta	x (xx.x%)	x (xx.x%)	x (xx.x%)	x (xx.x%)
	Delta	x (xx.x%)	x (xx.x%)	x (xx.x%)	x (xx.x%)
	BA.1	x (xx.x%)	x (xx.x%)	x (xx.x%)	x (xx.x%)
	BA.4/5	x (xx.x%)	x (xx.x%)	x (xx.x%)	x (xx.x%)
	XBB.1	x (xx.x%)	x (xx.x%)	x (xx.x%)	x (xx.x%)
Day 274 to Day 366	D614G	x (xx.x%)	x (xx.x%)	x (xx.x%)	x (xx.x%)
(n=x)	Beta	x (xx.x%)	x (xx.x%)	x (xx.x%)	x (xx.x%)
	Delta	x (xx.x%)	x (xx.x%)	x (xx.x%)	x (xx.x%)
	BA.1	x (xx.x%)	x (xx.x%)	x (xx.x%)	x (xx.x%)
	BA.4/5	x (xx.x%)	x (xx.x%)	x (xx.x%)	x (xx.x%)
	XBB.1	x (xx.x%)	x (xx.x%)	x (xx.x%)	x (xx.x%)
Any Time Point (n=x)	D614G	x (xx.x%)	x (xx.x%)	x (xx.x%)	x (xx.x%)
	Beta	x (xx.x%)	x (xx.x%)	x (xx.x%)	x (xx.x%)
	Delta	x (xx.x%)	x (xx.x%)	x (xx.x%)	x (xx.x%)
	BA.1	x (xx.x%)	x (xx.x%)	x (xx.x%)	x (xx.x%)
	BA.4/5	x (xx.x%)	x (xx.x%)	x (xx.x%)	x (xx.x%)
	XBB.1	x (xx.x%)	x (xx.x%)	x (xx.x%)	x (xx.x%)

n=Number of participants with reported infections and sequencing available at a given visit.

Tables with Similar Format:

Table 46:Number Participants with Breakthrough Infections by PANGO Call and Study Group,
Infected (by Self-Report or N-Protein) Cohort – mITT Population

[Implementation note: Update footnotes for N and n to state 'N=Number of infected participants in the Per Protocol population with sequencing done.' And 'n=Number of infected participants with reported infections and sequencing available at a given visit.']

Table 47:Number of Participants with Breakthrough Infections by PANGO Call and Study Group,
Uninfected (by Self-Report or N-Protein) Cohort – mITT Population

[Implementation note: Update footnotes for N and n to state 'N=Number of uninfected participants in the Per Protocol population with sequencing done.' And 'n=Number of uninfected participants with reported infections and sequencing available at a given visit.']

	Group 4E [Dosed Janssen, Boost Janssen] (N=X)	Group 5E [Dosed Moderna, Boost Janssen] (N=X)	Group 6E [Dosed Pfizer, Boost Janssen] (N=X)	All Participants (N=X)
Positive N-Protein Ab ELISA Among Those with A	Available Results ^a			
Day 1 - n/M (%)	x/x (x)	x/x (x)	x/x (x)	x/x (x)

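### Protocol 9.4.9 takes prior infection from the N-protein ELISA alone, so if the mucosal analyses are split, known infections with a negative N result would be counted as uninfected

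*Protocol*

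**What the plan says.** Protocol 9.4.9 plans summaries of mucosal responses "from nasal and salivary samples of participants in Cohort 2 who receive a second boost", and the correlation of those responses with serum responses, at each post-boost timepoint. It then says that the option of running these analyses "by status of prior infection (as given by N-protein ELISA assay) will be assessed". No visit or look-back period is given.

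Other parts of the protocol show that infection can be known in this cohort by other routes:

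- Section 4.1 says that "volunteers who contract symptomatic or asymptomatic COVID-19 between completion of their EUA primary series and the scheduled booster dose will be allowed" to stay on. The Synopsis and footnote d of Table 4 say the same. All three set a minimum interval between infection and booster, which presupposes that sites know when the infection occurred.
- Exclusion criterion 1 applies a known history of infection only to Cohort 1 and to the primary series of Cohort 2. Section 7.1.3 lists confirmed infection as a reason to stop dosing only before Dose 2.
- Section 8.1.3 calls for PCR swabs at illness visits. Follow-up of asymptomatic positives is optional.
- Section 9.4.9 itself has NAAT-confirmed infections sequenced, in the paragraph just before the mucosal one.

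The supplied SAP uses a two-source rule for other purposes. SAP 6.3.4 excludes from the per-protocol immunogenicity analysis any "Breakthrough COVID-19 infection either self-reported or Positive N-antibody test". The title of Table 47 in Appendix 1 ends "Uninfected (by Self-Report or N-Protein) Cohort – mITT Population", and Table 46 carries the matching infected label.

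**The concern.** The split is meant to separate people whose mucosal response reflects vaccination alone from people whose response also reflects infection. With N-antibody as the only criterion, a participant could have an infection confirmed by PCR, and even sequenced under the same section, and still be counted as not previously infected.

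Because no visit is named, a person who was N-positive earlier and negative near Day 1C could be handled the same way. The SAP's Table 48 shell, written for Cohort 1, lists such patterns (for example PNNNN and NPNNN), so the study's own tables allow for loss of N-positivity.

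If infection raises mucosal titres, these people lift the geometric mean (GM) of the uninfected stratum and shrink the contrast. Mixing them in can also distort the mucosal-serum correlation within that stratum. No primary endpoint is affected.

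**Working it through.** The plan gives no figure to reproduce: it states no ELISA sensitivity, infection prevalence or misclassification rate. What follows is illustration on stated assumptions.

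**Inputs (all assumed).** p = share previously infected by Day 1C; s = sensitivity of the N ELISA for past infection; r = share of N-negative infections that are known from report or PCR; k = ratio of titres, infected to uninfected. False-positive N results are ignored, and k is taken to be the same in N-negative as in N-positive infected people.

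**Step 1. Infected share of the N-negative stratum under the 9.4.9 rule:** c = p(1 − s) / [p(1 − s) + (1 − p)].

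- p = 0.3, s = 0.9: 0.03 / (0.03 + 0.70) = 0.041.
- p = 0.5, s = 0.7: 0.15 / (0.15 + 0.50) = 0.231.

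**Step 2. Effect on the stratum's GM and on the contrast.** The GM is multiplied by k^c, and the observed ratio becomes k^(1 − c).

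| k | c | GM multiplied by | Observed ratio |
|---|---|---|---|
| 4 | 0.041 | 1.06 | 3.8 |
| 4 | 0.231 | 1.38 | 2.9 |
| 2 | 0.041 | 1.03 | 1.9 |
| 2 | 0.231 | 1.17 | 1.7 |

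**Step 3. What a two-source rule would remove.** The infected share left in the stratum is p(1 − s)(1 − r) / [p(1 − s)(1 − r) + (1 − p)].

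- r = 0.5 at the lower corner: 0.015 / (0.015 + 0.70) = 0.021, down from 0.041.
- r = 0.5 at the upper corner: 0.075 / (0.075 + 0.50) = 0.130, down from 0.231.
- r = 1: zero in both. r = 0: no change.

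Step 1 is therefore the most the fix could remove for given p and s, reached only when every N-negative infection is otherwise known. Section 8.1.3 leaves sites wide discretion and makes visits for asymptomatic positives optional, so r may be well below 1.

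**Step 4. A wider grid.** Take p = 20%, 40%, 60% and s = 60%, 80%, 95%, with all 250 planned Cohort 2 participants. This overstates the count, since the number receiving a second boost is not given. The 9.4.9 rule places 2.5 to 60 infected people in the N-negative stratum, or 1.2% to 37.5% of it. At the midpoint (p = 40%, s = 80%) it is 20 of 170, or 11.8%. At k = 3 the GM is multiplied by 1.01 to 1.51 (midpoint 1.14). With r = 0.5 the infected share falls to 0.6% to 23.1%.

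The direction is clear if infection raises titres. The size depends almost entirely on unknown inputs.

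**The case against.** A reader might infer that protocol and SAP contradict each other on who counts as infected. The documents do not support that. SAP 6.3 states: "Analyses in the plan will only include participants who received the delayed Janssen-Ad26.COV2.S booster vaccine, study groups 4E, 5E and 6E". SAP 2.1 describes "five complementary CSRs with each CSR having a corresponding SAP", and one of these CSRs is for Cohort 2; its SAP is not among the documents and may already settle the rule. The supplied SAP repeats the mucosal objective but plans no mucosal analysis. Its two-source rule concerns breakthrough infection, for a per-protocol exclusion and for sequencing tables. Different rules for different purposes are not an inconsistency. SAP 6.3.4 also mentions neither PCR nor a Day 1C cut-off, so it is a precedent within the study and only an approximate one.

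Two further points can be made. The analysis is exploratory and descriptive, and the footnote to Protocol Table 7 says exploratory assays may be performed, not that they will be. And N serology is objective and can be applied uniformly, whereas self-report depends on who tested and how actively a site followed up; Protocol 9.2.1 itself refers to serological evidence of prior infection.

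All of this bears on framing and severity, and it stands. It does not rescue an N-only rule. A PCR-confirmed infection is not made doubtful by a negative N result, and adding a second source keeps the serology while correcting known errors.

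**Conclusion.** The point holds in a narrow form. Protocol 9.4.9 ties prior infection to one assay and no visit, in a cohort where infections can be known by report or PCR. If the split is run on that wording, known N-negative infections go to the wrong stratum.

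It would be too strong to say that participants will be misclassified. The protocol commits only to considering the split, so the error is conditional on its being done.

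The size is not established. The 4-23% range rests on assumed prevalence of 30-50% and sensitivity of 70-90%; the GM inflation of 6-38% (4-fold) or 3-17% (2-fold) rests on an assumed titre ratio as well. Both are upper limits, under those assumptions, on what the fix could remove. Severity is low: no primary endpoint or hypothesis test depends on this analysis. It is worth correcting because it is cheap, and because fixing the rule in advance avoids choosing a definition after results are seen in an open-label study.

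**What to change.** In Protocol 9.4.9, or in the Cohort 2 SAP without a protocol amendment, state: for the second-boost mucosal analyses, prior infection means any positive N-protein result up to and including Day 1C, or any reported or PCR-confirmed SARS-CoV-2 infection before Day 1C; all others are classed as without evidence of prior infection.

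The cost is one sentence and no new sampling. The documents do not say at which Cohort 2 visits the N ELISA is run, so the SAP should also list the visits that contribute. The downside is that a false self-report would move an uninfected person to the infected stratum. Infections that were neither reported nor detected by PCR or N-antibody stay in the other stratum under either rule, and the report should say so.

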10 SUPPORTING DOCUMENTATION AND OPERATIONAL CONSIDERATIONS

10.1 Regulatory, Ethical, and Study Oversight Considerations

This study will be conducted in conformity with the principles set forth in The Belmont Report: Ethical Principles and Guidelines for the Protection of Human Subjects of Research (US National Commission for the Protection of Human Subjects of Biomedical and Behavioral Research; April 18, 1979), and the federal policy for the Protection of Human Subjects codified in 45 CFR Part 46, 21 CFR Part 50 (Protection of Human Subjects), and the ICH E6(R2).

An OHRP-registered IRB will review and approve this protocol, associated informed consent documents, recruitment materials, and handouts or surveys intended for the subjects, prior to the recruitment, screening and enrollment of subjects. The IRB review shall be in accordance with 45 CFR 46 and 21 CFR 50, 21 CFR 56 (IRBs), and other federal, state, and local regulations and policies, as applicable.

Each institution engaged in this research will hold an OHRP-approved FWA.

Any amendments to the protocol or informed consent documents will be approved by the IRB before they are implemented. IRB review and approval will occur at least annually throughout the duration of the study. The participating site PI will notify the IRB of deviations from the protocol and reportable SAEs, as applicable to the IRB policy.

DMID must receive the documentation that verifies IRB approval for this protocol, informed consent documents and associated documents, prior to the recruitment, screening and enrollment of subjects, and any IRB approvals for continuing review or amendments as required by the DMID.

10.1.1 Informed Consent Process

Informed consent is a process that is initiated prior to an individual agreeing to participate in a trial and continuing throughout the individual's trial participation. Investigators or designated research staff will obtain a subject's informed consent in accordance with the requirements of 45 CFR 46, 21 CFR 50 and 21 CFR 56 for FDA-regulated studies, state and local regulations and policy, and ICH E6 GCP before any study procedures or data collection are performed. The participating site PI or other study staff may obtain oral or written information for the purpose of screening, recruiting, or determining the eligibility of prospective subjects without the informed consent of the prospective subject if the process is approved by the IRB.

At the first study visit, informed consent will be obtained and documented before any study procedures are performed. Subjects will receive a concise and focused presentation of key information about the clinical trial, verbally and with a written consent form. The key information about the purpose of the study, the procedures and experimental aspects of the study, study interventions/products, risks and discomforts, the expected duration of the subject's participation in the trial, any expected benefits to the subject, and alternative treatments and procedures that may be available to the subject. The explanation will be organized and presented

in lay terminology and language that facilitates understanding why one might or might not want to participate.

Subjects will receive an explanation as to whether any compensation and any medical treatments are available if injury occurs, and, if so, what they consist of, or where further information may be obtained. Subjects will be informed of the anticipated financial expenses, if any, to the subject for participating in the trial, as well as any anticipated prorated payments, if any, to the subject for participating in the trial. They will be informed of whom to contact (e.g., the participating site PI) for answers to any questions relating to the research project. Information will also include the foreseeable circumstances and/or reasons under which the subject's participation in the trial may be terminated. The subjects will be informed that participation is voluntary and that they are free to withdraw from the study for any reason at any time without penalty or loss of benefits to which the subject is otherwise entitled. Subjects will be allowed sufficient time to consider participation in this research trial and have the opportunity to discuss this trial with their family, friends or legally authorized representative, or think about it prior to agreeing to participate.

Subjects will be informed that records identifying the subject will be kept confidential, and, to the extent permitted by the applicable laws and/or regulations, will not be made publicly available. If the results of the trial are published, the subject's identity will remain confidential. Subjects will be informed, even if identifiers are removed, that information collected from this research and/or specimens may be used for secondary research, including the sharing of deidentified data.

Subjects will be informed that the monitor(s), auditors(s), IRB, NIAID, and regulatory authority(ies) will be granted direct access to the subject's original medical records for verification of clinical trial procedures and/or data without violating the confidentiality of the subject, to the extent permitted by the applicable laws and regulations, and that, by signing a written ICF, the subject is authorizing such access.

ICFs will be IRB-approved, and subjects will be asked to read and review the consent form. Subjects must sign the ICF prior to starting any study procedures being done specifically for this trial. Once signed, a copy of the ICF will be given to the subject for their records.

New information will be communicated by the participating site PI to subjects who consent to participate in this trial in accordance with IRB requirements. The informed consent document will be updated, and subjects will be re-consented per IRB requirements, if necessary.

10.1.1.1 Requirements for Permission by Parents/Guardians and Assent by Children (in case of a minor)

Not Applicable

10.1.1.2 Other Informed Consent Procedures

The rights and privacy of human subjects who participate in genomic or phenotypic research studies will be protected at all times. The consent process, including relevant language in the ICF, will provide an explanation of the potential risks to the individual study subjects and their families. Clinical metadata, genomic, or other datasets or a subset of the clinical and other metadata that may potentially identify human subjects will not be released in unrestricted

databases. Subjects will be informed that the evolution of genomic technology and analytical methods raises the risk of re-identification, even when specimens are de-identified.

Subjects will be asked for consent to collect additional blood, nasal or NP swabs, the use of residual specimens, and the sharing of genetic information and samples for secondary research. This extra/residual blood and corresponding serum, plasma and PBMCs, and mucosal samples will be used as back-up specimens for PP defined assays or designated for secondary research use and stored indefinitely at a designated storage facility.

Subjects will be asked to consent specifically to genetic testing on primary and secondary research samples, including but not limited to transcriptomics and DNA sequencing. DNA sequencing data will be kept private. DNA data may be used to produce commercial antibody-based therapeutics. Subjects will not share in profits or commercial rights to those products.

If subjects choose not to provide permission for extra blood and secondary research use, they will not be eligible for enrollment into the study.

Collection of extra/residual samples during the course of the study will help facilitate rapid follow-on analyses, if warranted, to provide more comprehensive scientific insights into the impact (safety and immunological) of the vaccine on the host response to vaccination. To maintain statistical power in follow-on analyses it is important that extra blood collection and secondary research use be included in as many subjects as possible, due to the limited sample size per treatment arm.

The stored samples will be labeled with barcodes to maintain confidentiality. Research with identifiable samples and data may occur as needed, however, subject confidentiality will be maintained as described for this protocol and with IRB approval.

Samples designated for secondary research use may be used for additional immunological assessments that may include but are not limited to antibody epitope mapping, B and T cell repertoire determination, non-traditional immune assay development, determination of innate immune factors and the ability of vaccine-induced antibodies to cross-react to different proteins and virus strains. These blood samples might be used in new or different immunological laboratory tests, to provide information for the development of new vaccines or therapeutics, or for the studies of SARS-CoV-2 or other infections. Secondary research using DNA may also be warranted to understand genetic factors involved in vaccination failures.

Samples will not be sold for commercial profit. Although the results of any future research may be patentable or have commercial profit, subjects will have no legal or financial interest in any commercial development resulting from any future research.

There are no direct benefits to the subject for extra specimens collected or from the secondary research. No results from secondary research will be entered into the subject's medical record. Incidental findings will not be shared with the subject, including medically actionable incidental findings, unless required by law.

Risks are associated with the additional volume of blood collected, such as anemia. Risks for loss of privacy and confidentiality are described below.

Subjects may withdraw permission to use samples for secondary use at any time. They will need to contact the participating site and the samples will be removed from the study repository after this study is completed and documentation will be completed that outlines the reason for withdrawal of permission for secondary use of samples. Subjects who withdraw consent before the last visit will not have the extra blood drawn for secondary use.

Human Genetic Testing

The research staff will seek the subjects' consent for extra and residual specimens to be stored and used for secondary research, including genetic research, evaluating human genomic and phenotypic markers. The rights and privacy of human subjects who participate in genomic or phenotypic research studies will be protected at all times.

The consent process will include an explanation of the potential risks to the individual subjects and their families associated with data submitted to an NIH data repository and subsequent sharing. Data that may potentially identify human subjects will not be released in unrestricted databases. Subjects will be informed that the evolution of genomic technology and analytical methods raises the risk of re-identification, even when specimens are de-identified. The consent will include whether individual subject data will be shared through a NIH controlled access data repository. Data for genomic or phenotypic research will be submitted to a controlled access data repository, therefore, informed consent permitting the data sharing must be documented, even if the specimens are de-identified.

